2.0 Research Reference Numbers

IRAS Number:	252155
EudraCT Number:	2019-001587-30
ISRCTN Number / Clinical trials.gov Number:	ТВС

5.0 Trial Summary

Full title	AZD1656 in Transplantation with Diabetes tO PromoTe Immune TOleraNce
Short title and/or Acronym	The ADOPTION Study
Trial Design	Single site, placebo controlled, double blind randomised
Methodology	clinical trial.
Phase of the Trial	11
Study Duration	27 months
Study setting	Single NHS site
Investigational Medicinal Product(s)	AZD1656
Medical condition or disease under investigation	Post-renal transplant diabetes and graft rejection
Planned Sample Size	50
(Maximum) Treatment duration	3 months
Follow up duration	9 months
End of Trial definition	The last patient has completed their last follow up point at 1 year post-transplant (data review visit).

27.1 Amendments	
27.2 Access to the final trial dataset	
28.0 Trial Committees	
29.0 Publication and Dissemination Policy	
29.1 Publication	
29.2 Dissemination policy	
30.0 References	

8.0 List of Abbreviations / Glossary of Terms

AE	Adverse event
APR	Annual Progress Report
AR	Adverse reaction
AUC	Area under curve
BMI	Body mass index
BP	Blood pressure
CI	Chief investigator
CKD	Chronic kidney disease
C _{max}	Maximum concentration
СТА	Clinical Trial Authorisation
CMV	Cytomegalovirus
CRF	Case report form
DSM	Drug safety monitoring
DSUR	Development Annual Safety Update
ECD	Extended Criteria Donor
ECG	Electrocardiogram
eCRF	Electronic case report form
eGFR	Estimated Glomerular Filtration Rate
EOT	End of trial
FACS	Fluorescent-activated cell sorting
GCP	Good Clinical Practice
HbA1c	Haemoglobin A1c
HDL	High-density lipoprotein
HLA	Human leukocyte antigen
HOMA	Homeostatic model assessment
HOMA IR	Homeostatic model assessment of insulin resistance
HRA	Health Research Authority
IB	Investigator brochure
ID	Identifier
IMP	Investigational medical product
IRAS	Integrated Research Approval System
ISF	Investigator site file
ITT	Intention to treat
JRMO	Joint research management office (Sponsor)
LDL	Low-density lipoprotein
MHRA	Medicines and Healthcare products Regulatory Agency
mTORC2	Mammalian target of rapamycin complex 2
NHS	National Health Service
NICE	The National Institute for Health and Care Excellence
ONS	Office for National Statistics

ULNUpper limit of normalUKASUnited Kingdom Accreditation Service	PD PI PI3K-Akt PIS PK QMUL R&D REC RLH SAE SAP SAR SAP SAR SOP SUB-I SUSAR T _{1/2} Treg TSC	Pharmacodynamics Primary investigator Phosphoinositide 3-kinase – Protein kinase B Patient information sheet Pharmacokinetics Queen Mary University of London Research and Development Research Ethics Committee Royal London Hospital Serious adverse event Statistical analysis plan Serious adverse reaction Standard operating procedure Sub investigator Serious unexpected serious adverse reaction Half-life Thymic regulatory T cells Trial steering committee
UKAS United Kingdom Accreditation Service	TSC	Trial steering committee
	UKAS	

9.0 Introduction

9.1 Background

Renal Transplantation and glucose control

Type 2 diabetes is the most common cause of end-stage renal failure in the UK. Kidney transplantation is widely held to be the optimal form of renal replacement therapy for patients with end-stage renal disease, leading to a longer survival and improved quality of life in patients receiving a renal transplant compared to those that remain on dialysis (Reese et al, 2015).

However transplantation leads to a higher glucose burden in patients. This has been associated with acute rejection, sepsis and worse outcomes, and patients frequently have to increase their anti-diabetic medication in the early post-transplant period.

One reason for this is that immunosuppressive medications (glucocorticoids and calcineurin inhibitors) can lead directly to hyperglycaemia. In addition, as renal function improves, there is greater renal clearance of anti-diabetic agents and endogenous insulin leading to a reduced potency of these medications. These effects are most pronounced within the early post-transplant period, as this is the period when the immunosuppressive burden is the strongest and the changes in renal function most marked.

The role of Glucokinase in glucose control

Glucokinase is an enzyme which has two effects to lower glucose. In the pancreas, beta cells control insulin secretion. In pancreatic beta cells glucokinase converts glucose to glucose-6-phosphate, which is a rate-limiting step in the secretion of insulin; as such, increased glucokinase activity leads to more insulin secretion. Secondly, in the liver, glucokinase increases hepatic uptake of glucose (Scheen, 2018). Defective glucose-induced insulin secretion and increased hepatic glucose output are of the hallmarks of type 2 diabetes. Because of these effects, glucokinase activators have been promising therapeutics for type 2 diabetes for almost two decades.

One agent studied is AZD1656: a potent, selective activator of human glucokinase. Twenty-five clinical studies have been completed to evaluate the safety, tolerability, pharmacokinetics (PK), pharmacodynamics (PD) and drug interactions with AZD1656. Approximately 960 subjects have been exposed to AZD1656 in 25 clinical studies covering phase I to phase IIb as part of a global development program by AstraZeneca. Single oral doses of AZD1656 up to 180 mg have been given to healthy volunteers during euglycaemic clamp conditions (Ericsson et al, 2012). Patients with type 2 diabetes have been administered single oral doses up to 450 mg; and also daily doses of 10 to 200 mg have been given to

patients with type 2 diabetes for up to 6 months' duration. AZD1656 has been shown to be a, well-tolerated medication in patients with type 2 diabetes and no safety concerns were raised in studies up to 6 months. Unfortunately, the anti-diabetic effect of AZD1656 has been found to wear off after several months, thus limiting its long-term use for patients with diabetes (Kiyosue et al, 2013; Wilding et al, 2013).

A shorter course of AZD1656 may be of benefit in controlling the glucose levels of patients with diabetes during the time shortly after renal transplantation when the immunosuppressive burden, and hence gluconeogenesis, is greatest. In addition, AZD1656 may have other benefits post-renal transplantation in an unrelated action to its anti-diabetic action, which involve its effects on immune function.

Treg cells in renal transplantation and tissue injury

Thymic regulatory T (Treg) cells are a subpopulation of T cells that modulate the immune system. These cells have immunosuppressive functions and downregulate other effector T cell populations. As such, they are instrumental for the maintenance of tolerance to self-antigens. A crucial step in their immuno-modulatory function is the ability of active Treg cells to migrate in the body and, during inflammation, to home on inflamed tissue (Tang et al, 2004; Kishore et al, 2017).

In transplantation a major unmet need is to develop management strategies to prevent both acute and chronic rejection which are associated with poorer graft survival. Current therapies to minimise rejection rates have their own side effects including direct renal and pancreatic toxicity and the progression of cardiovascular disease. Treg cells are an attractive potential therapy for transplantation to reduce the immunosuppressive burden (Zwang et al, 2017). Evidence for the role of Treg cells' beneficial effects in transplantation is suggested by data which demonstrates that Treg cells directly reduce inflammation and reperfusion injury in kidneys (Kinsey et al, 2009; Hu et al, 2016).

Furthermore Treg cells suppress immune function *in vitro*, and are associated with transplant acceptance in kidney transplant patients (Daniel et al, 2012). High levels of Treg cells positively correlate with renal allograft survival and function (Schaier et al, 2012). In addition, in renal biopsies, Treg infiltration is associated with better graft function (Bestard et al, 2008). Finally, there is evidence of tissue protection in transplantation mouse models following transfer of humanised Treg cells (Yi et al, 2012). Therefore, Treg cell proliferation and activation may hold the keys to unlock the future promise of immune tolerance which is the 'Holy Grail' of transplant immunology: the potential to be able to perform solid organ transplants without the need for long term immunosuppression with all the advantages that this would bring.

Role of glucokinase in Treg biology

Recent data combines the two streams of research involving glucokinase biology, in the fields of immunosuppression and glucose lowering effects. As well as being

involved in glucose homeostasis, glucokinase has been shown to increase Treg migration and trafficking. Treg migration has been shown to be dependent on glycolysis which is mediated via the PI3K-Akt pathway and activation of mTORC2. mTORC2 in turn induces glucokinase expression which appears to be necessary for Treg migration. AZD1656 has been demonstrated to increase glucokinase activity, thus leading to reduced numbers of circulating Treg cells, with the hypothesis that they have been activated and migrated into the inflamed tissues (Kishore et al, 2017). Further evidence for the role of glucokinase comes from data demonstrating that inhibition of glucokinase resulted in less Treg motility, leading to increased rejection in a skin transplant animal model. In addition, humans who have reduced inhibition of glucokinase due to a mutation in a glucokinase regulatory protein have been shown to have increased motility and decreased circulating numbers (Kishore et al, 2017).

9.2 Assessment and management of risk

Standard of care

Renal transplantation is not without risk; however, overall the benefit of a functioning renal transplant outweighs the risks of remaining on dialysis.

Patients in this study will have all their pre- and post-transplant care as per usual clinical care, with the exception of the following intervention: treatment with AZD1656 or placebo for 3 months post-renal transplant.

The standard of care follow up is that patients attend clinic twice a week for the first 6 weeks post-transplant, then weekly for another 6 weeks, they remain on weekly or fortnightly clinic visits for a further 12 weeks, after which point depending on the stability of the patients graft function they reduce clinic visits to every 2-4 weeks up to one year.

As with all patients with diabetes who have had a renal transplant, there is the risk of both hypoglycaemia and hyperglycaemia due to changing renal function and new medications which may alter glucose levels. Because of this, we measure patient's glucose levels and diabetic control routinely when they are seen frequently in clinic and enquire as to any episodes of hypo or hyperglycaemia. The transplant clinician may alter patient's anti-diabetic medications to maintain optimal glycaemic control as part of routine care.

Risks associated with AZD1656 The known risks to human subjects.

Justification for the choice of route of administration, dosage, dosage regimen, and treatment period(s)

We are using a dose within the higher range that has shown to be safe and efficacious in clinical studies. We do not have human T reg efficacy data: therefore as this is an exploratory study, this is scientifically a good dose to use. We would therefore not up-titrate from this dose. We are working on the hypothesis that the pharmacodynamic effect of AZD1656 on Treg migration activity is the same as for glucose lowering (we have no evidence to suggest this is not correct), and we proposed using what we know is an effective and safe dose in order to adequately test the hypothesis. We have chosen not to start at and lower dose and subsequently up-titrate the dose: given the proposed mechanism of action of AZD1656, early mobilisation of regulatory T cells with subsequent amelioration of renal ischaemia-reperfusion injury is required in order to benefit the new transplant. We are measuring delayed graft function as one of the secondary clinical endpoints as a surrogate for improved renal outcome within the first 7 days.

From a safety perspective, all of the patients will be diabetic and induction therapy given for renal transplantation is associated with hyperglycaemia; in addition as the patients are inpatients for the first 5-7 days post transplant (and during initiation of study drug) they are closely monitored for hypoglycaemia. The risk of hypoglycaemia after this period is low based on the data from the previous Phase 2 diabetes studies with AZD1656. If recurrent hypoglycaemia occurs despite removal of other anti-diabetic medications, then the study medication will be withdrawn as per withdrawal criteria.

Preclinical & Clinical Data

Investigator's Brochure AZD1656, Edition 9, September 2020

Twenty-five clinical studies have been completed to evaluate the safety, tolerability, PK, PD and drug interactions with AZD1656. Approximately 960 subjects have been exposed to AZD1656 for up to 6 months' duration. In patients with type 2 diabetes and renal impairment, the PK and PD effects after single doses of AZD1656 were comparable to diabetic patients with normal renal function.

Across clinical studies, AZD1656 has been well tolerated and no safety concerns have been raised. No safety signals have been identified regarding vital signs, ECG, weight, BMI and physical findings.

There have been no treatment related changes in safety laboratory variables including muscle biomarkers and liver function tests in Phase I to IIa. From the few cases with increased liver enzymes in Phase IIb, a minor increase from AZD1656 treatments could not be excluded.

AZD1656 is mainly metabolised via CYP2C8, therefore potent inhibitors of CYP2C8 (e.g. gemfibrozil) may increase exposure to this drug (AUC).

Other than inhibitors of CYP2C8, no significant drug-drug interactions have been reported in phase I/II clinical trials; however there may be drug-drug interactions that are as yet unknown.

Reproductive restrictions

No data is available on the effects of AZD1656 on pregnancy and lactation in humans. Preclinical studies have shown that AZD1656 is not genotoxic. There was no effect on male fertility in rat. Overall, the effects of AZD1656 on embryofoetal development seen in pre-clinical studies were considered to be secondary to maternal hypoglycaemia. Results from the preclinical repro-toxicity studies support inclusion of women of childbearing potential in clinical studies, provided that pregnancy is prevented using a highly effective form of contraception. In case of pregnancy during the study, treatment should be stopped.

How the risk will be minimised/managed

Hypoglycaemia:

As with most anti-diabetic medications there is a risk of hypoglycaemia. However, following a renal transplant, given the increased glucose production from the steroid medications along with increased insulin metabolism, hyperglycaemia rather than hypoglycaemia is more of an issue. For AZD1656, in phase I to IIa, few hypoglycaemic events have been reported and only rarely with a plasma glucose level below 3 mmol/L (54 mg/dL). In phase IIb, the proportion of patients reporting hypoglycaemic events was overall small. Fewer patients in the AZD1656 treatment groups reported hypoglycaemic events compared to the glipizide group. Low glucose levels were either asymptomatic (detected in scheduled measurement) or associated with mild symptoms, and in all cases manageable by the patients. All events with low plasma glucose have responded rapidly to carbohydrate intake.

All patients will be seen frequently in a specialist post-transplant clinic where, as part of their standard of care, they will have their blood glucose measured regularly along with makers of diabetic control including HbA1c. The patient will be given instructions to measure blood glucose if they get symptoms of hyperglycaemia (e.g. thirst, polyuria) or hypoglycaemia (cold sweat, dizziness). If a major hypoglycaemic event occurs, or more than one minor event since last visit, the patient will be told to contact the investigator before the next visit.

As with all patients with diabetes post-transplant, if a patient's blood glucose control is considered by their clinical team to be too high or low, then their regular antidiabetic medications will be altered to achieve diabetic control targets as per our

standard of clinical care. National guidelines in the management of CKD patients with diabetes suggest controlling the HbA1c to between 6.5% (48mmol/mol) to 8.5% (68mmol/mol). Within this range there are suggestions to aim for tighter control (towards 6.5%) or less tight control (towards 8.5%) on an individualised patient basis (Renal Association 2018).

Reproductive restrictions

Female study participants

Women of child-bearing potential are permitted to participate in this study provided that they agree to avoid pregnancy through the use of a highly effective form of contraception starting from the time of study enrolment until the final safety follow-up visit has been completed (2 weeks after cessation of study medication). AZD1656 has low potential for drug-drug interaction through induction of any of the CYP enzymes so an interaction with hormonal contraception is not anticipated. Methods of highly effective contraception are outlined in section 12.2 (Exclusion criteria). If a female participant should become pregnant, then the study medication will be stopped. She will be asked to consent to the collection of data about her pregnancy, and the birth and health of her baby.

Male study participants

It is important that women of childbearing potential, who are the partners of male patients, do not become pregnant during the study and until the participant has completed the safety follow up visit.

All male study participants should avoid fathering a child by using an effective method of contraception together with their female partner/spouse, starting from the time of study enrolment until the final safety follow-up visit has been completed. In this scenario, we have advised the use of a condom and female partners to use a method of highly effective contraception. If a female partner of a male patient should become pregnant, then she will also be asked to consent to the collection of data about her pregnancy, and the birth and health of her baby.

For male patients whose partner is pregnant, the man should use a condom for the duration of the study and until the final safety follow-up visit has been completed.

Sperm Donation

Male patients should not donate sperm for the duration of their participation in the study and until they have completed the study follow-up visit.

This trial is categorised as: Type C

[figure not shown]
9.3 Rationale for study design

Our hypothesis is that treatment with AZD1656 may lead to increased Treg localisation to the transplant kidney in the early post-operative course. This may lead to reduced ischaemia reperfusion injury through the immunosuppressive effects of Tregs, measurable by a change in the incidence of delayed grant function. At 3 months we hypothesize that AZD1656 may lead to increased Treg cell localisation in the transplanted kidney, as a marker for improved graft survival. We will measure peripheral Treg population as a marker for Treg trafficking to the kidney as this can be measured serially with minimal risk to the patient. We will include histological parameters from the standard of care 3 month protocol biopsy as a key secondary endpoint. Finally, we hypothesize that AZD1656 may be an effective and safe adjunct for the early management of diabetes post-renal transplant.

We propose an exploratory phase 2 study, examining the efficacy and safety of 3 months' treatment with AZD1656 100mg twice daily in patients with diabetes undergoing renal transplantation in a tertiary renal unit.

10.0 Trial Flowchart

11.0 Trial Objectives and Design

11.1 Primary Objective/s

To determine whether treating post-transplant patients with AZD1656 compared to placebo for 3 months leads to altered Treg migration.

11.2 Secondary Objective/s

To determine the safety and efficacy of AZD1656 to control diabetes post-transplant. To investigate the effect of AZD1656 on Treg cell infiltration in renal transplant tissue.

11.3 Endpoints11.3.1 Primary Endpoint

The primary endpoint is the change in mean peripheral Treg cell number between baseline and 3 months measured using flow cytometry analysis (FACS) between AZD1656 and placebo.

11.3.2 Secondary Endpoints

- 1) Histological staining for Treg cells in renal biopsy tissue between baseline and 3 month protocol biopsy
- 2) Incidence of delayed graft function, defined as the need for dialysis within 1 week post-transplant
- 3) Diabetic control between baseline and month 3 using change in HbA1c measurement
- 4) Dose of other anti-diabetic medication between baseline and month 3 (descriptive)
- 5) Safety endpoints: i.e. number of hypoglycaemic episodes (descriptive)
- 6) Insulin resistance: HOMA IR measurement at month 3
- 7) Graft function: (eGFR) at month 3
- 8) Episodes of acute rejection (defined as biopsy proven acute rejection)
- 9) Episodes of opportunistic infections: bacterial and viral (descriptive)

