12.1 Inclusion Criteria

- a) Females or males aged 18 years and above
- b) Having undergone renal transplantation at the Royal London Hospital within the previous 24 hours
- c) A pre-transplant diagnosis of Type 2 diabetes
- d) Provision of written, informed consent prior to any study specific procedures
- e) In women of childbearing potential* documentation of a negative pregnancy test during admission for renal transplant.

*Women of childbearing potential are defined as women following menarche until becoming post-menopausal, unless permanently sterile. Permanent sterilisation methods include hysterectomy, bilateral salpingectomy and bilateral oophorectomy. A post-menopausal state is defined as the absence of menses for 12 months without an alternative medical cause.

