13.2 Informed Consent Procedures

Informed consent will be obtained either pre-transplantation or within 24 hours posttransplantation, but prior to the participant undergoing procedures that are specific to the trial, and are outside standard routine care at the participating site (including the collection of identifiable participant data).

In the case of deceased donor transplantation, patients do not know when they will receive a transplant, and it is therefore impossible to approach patients in the days and weeks before their transplant. Patients will have already given consent to undergo their renal transplant at short notice, however some patients may be unable to give fully informed consent in the time immediately before or within 24 hours after transplant for this research study. If the PI or patient feels they are unable to give fully informed consent within the first 24 hours after the operation, then they will not be consented.

Patients who are planned to undergo live-donor transplantation will be given information about the study pre-transplantation during the assessment process, but will not be consented until they proceed with the transplant.

We hold regular pre-transplant open days to which all patients on the transplant waiting list are invited. At these open days we will inform patients of the current study opportunities. We will use the PIS as the text for these discussions and will be free to verbally discuss the study with patients on the day.

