13.7.2 Trial assessments

Screening visit

Informed consent Inclusion/exclusion criteria

Documentation of a negative pregnancy test from pre-transplant care

In women of childbearing potential: defined as women following menarche until becoming post-menopausal, unless permanently sterile. Permanent sterilisation methods include hysterectomy, bilateral salpingectomy and bilateral oophorectomy. A postmenopausal state is defined as the absence of menses for 12 months without an alternative medical cause.

Medical history

Demographic data

Concomitant medication

Visit 1 - to occur within 24 hours post-transplant

Inclusion/exclusion criteria

Transplant data

Documentation of a negative pregnancy test

Concomitant medication

Targeted physical examination

Adverse event reporting

Laboratory bloods: including fasting c-peptide, cholesterol and serum glucose; serum urea and electrolytes (including creatinine), albumin, alkaline phosphatase (ALP), bilirubin, alanine aminotransferase (ALT), bone profile and C-reactive protein; haemoglobin and HbA1c; and serum save. Results from bloods that have been taken as part of routine care may also be included on the case record forms.

20ml of blood will also be taken for peripheral Treg quantification.

Vital signs recording

Weight

Randomisation

Study drug dispense

In addition, the renal biopsy specimen collected as per clinical care at time of biopsy will be stained for Treg cell markers.

Visit 2 (1 week post randomisation +/- 3 days))

Check drug adherence Concomitant medication Documentation of a negative pregnancy test Targeted physical examination Weight Vital signs recording

Fasting blood tests: including fasting c-peptide, cholesterol and serum glucose; serum urea and electrolytes (including creatinine), albumin, alkaline phosphatase (ALP), bilirubin, alanine aminotransferase (ALT), bone profile and C-reactive protein; haemoglobin and HbA1c and serum save. Results from bloods that have been taken as part of routine care may also be included on the case record forms. 20ml of blood will also be taken for peripheral Treg quantification.

Adverse event reporting

Visit 3 (2 weeks post randomisation +/- 3 days)

Activities as per visit 2 with exception of blood collection for Treg quantification

Visit 4 (4 weeks post randomisation +/- 3 days)

Activities as per visit 3

Visit 5 (8 weeks post randomisation +/- 1 week)

Activities as per visit 3

Visit 6 (12 week post randomisation +/- 1 week)

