15.13 Dosage schedules

The patient will be dispensed either placebo or AZD1656 tablets for a 3 month supply.

These are two 50mg oral tablets to be taken twice a day with or after meals.

Missed doses will be permitted: if a patient misses a dose they should take their next dose at the usual time. Drug adherence will be encouraged at each visit. Drug accountability will be assessed at each study visit where patients will bring back their unused supply with non-adherence defined as less than 80% or more than 120% of medications taken.

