19.3 Statistical analysis plan (SAP)

Please refer to SAP for full details

Primary Endpoint

The primary endpoint is the change in mean peripheral Treg cell number between baseline and 3 months measured using FACS analysis between AZD1656 and placebo.

This will be analysed at the first data analysis.

Secondary Endpoints:

- 1) Histological staining for Treg cells in renal biopsy tissue between baseline and 3 month protocol biopsy
- Incidence of delayed graft function, defined as the need for dialysis within 1 week post-transplant
- 3) Diabetic control between baseline and month 3 using change in HbA1c measurement
- 4) Dose of other anti-diabetic medication between baseline and month 3 (descriptive)
- 5) Safety endpoints i.e. number of hypoglycaemic episodes (descriptive)
- 6) Insulin resistance: HOMA IR measurement at month 3
- 7) Graft function: (eGFR) at month 3
- 8) Episodes of acute rejection (defined as biopsy proven acute rejection)
- 9) Episodes of opportunistic infections: bacterial and viral (descriptive)

All of these endpoints will be analysed at the first data analysis; endpoints 8 and 9 will also be re-examined at the second data analysis.

Exploratory or Tertiary Endpoints/outcomes

- 1) 12-month graft function (eGFR) and diabetic control (HbA1c; medication review) to assess legacy effect (potential follow up publication)
- 2) Differences in other peripheral T cell populations, measured by FACS analysis
- 3) Histological staining for Treg cells in any renal biopsy taken for clinical indications between baseline and month 3 protocol biopsy
- 4) Differences in the functional phenotype of the Treg cells

Endpoints 2 and 3-4 will be analysed at the first data analysis; endpoint 1 will be analysed at the second data analysis.

Baseline Demographics and Biochemical parameters

Demographics and Clinical Characteristics

- Age at recruitment (derived from date of birth; continuous)
- Sex (categorical)
- Self-reported ethnicity (using ONS categories; categorical)
- Weight (continuous)
- Systolic BP (continuous)
- Diastolic BP (continuous)

Medical History

- Cause of end stage renal failure (categorical)
- Dialysis modality (categorical)
- Dialysis vintage (continuous)
- Diabetes duration (continuous)
- Retinopathy (yes/no, categorical)
- Neuropathy (yes/no, categorical)
- Coronary artery disease (yes/no, categorical)
- Peripheral artery disease (yes/no, categorical)
- Cerebrovascular disease (yes/no, categorical)

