- Hypertension (yes/no, categorical)
- Heart failure (yes/no, categorical)

Pregnancy test

• Pregnancy test negative (either serum or urine) (yes/no, categorical)

Transplant details

- Cold ischaemia time in hours (continuous)
- Warm ischaemic rime minutes (continuous)
- Donor age (continuous)
- ECD (yes/no, categorical)
- CMV mismatch (yes/no, categorical)
- HLA mismatch (categorical)

Medication

Each medication will be recorded as name/dose/start date (categorical)

Biochemical Parameters

- Fasting c-peptide (continuous)
- Fasting cholesterol (continuous)
- Haemoglobin (continuous)
- Serum sodium (continuous)
- Serum potassium (continuous)
- Serum urea (continuous)
- Serum creatinine (continuous)
- eGFR (CKD-EPI formula, continuous)
- Serum albumin (continuous)
- Serum alkaline phosphatase (continuous)
- Serum bilirubin (continuous)
- Serum alanine aminotransferase (continuous)
- Serum calcium (continuous)
- Serum phosphate (continuous)
- C-reactive protein (continuous)
- Glucose (continuous)
- Haemoglobin A1C (DCCT aligned; continuous)
- Peripheral Treg Cell number (interval)
- HOMA IR (continuous)

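### Delayed graft function is counted from transplant although randomisation may be up to 24 hours later, so dialysis given only before randomisation counts as an event that treatment could not have prevented (minor)

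*Combined protocol and SAP*

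**What the plan says.** Sections 11.3.2 and 19.3 define the endpoint in the same words: "Incidence of delayed graft function, defined as the need for dialysis within 1 week post-transplant". The clock starts at transplant.

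Entry to the trial comes after transplant. Section 12.1 requires "Having undergone renal transplantation at the Royal London Hospital within the previous 24 hours". Section 13.7.2 has "Visit 1 - to occur within 24 hours post-transplant" and lists randomisation and dispensing under that visit; the schedule in section 13.7.1 agrees. The 24 hours is a maximum. Section 13.2 says "Informed consent will be obtained either pre-transplantation or within 24 hours posttransplantation", so some patients could be randomised soon after surgery.

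On dosing, section 15.13 says "The patient will be dispensed either placebo or AZD1656 tablets for a 3 month supply". Neither it nor section 15.12 gives a time for the first dose.

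The baseline list in section 19.3 includes dialysis modality, dialysis vintage, ischaemia times and donor factors. It does not include dialysis between transplant and randomisation. The same section says "Please refer to SAP for full details".

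**The concern.** Sections 9.2 and 9.3 give delayed graft function a specific job. It is the clinical sign that early treatment has reduced ischaemia-reperfusion injury. Dialysis that took place before allocation cannot carry that signal. As defined, the endpoint mixes events that treatment might influence with some that it could not, and the planned baseline table would not show how many of the latter there were.

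At stake is the interpretation of one of nine secondary endpoints. Section 19.1 says the pilot is meant to supply data for a larger trial, so a risk ratio pulled towards 1 could be carried into that planning. The primary endpoint is not affected.

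**Working it through.** **Timing.** The endpoint window is 7 × 24 = 168 hours from transplant. Up to 24 of these, 24/168 = 14%, can precede randomisation. That is a share of time, not of events. The gap before first dose could be longer, since no first-dose time is set.

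**Is the early period set aside anywhere?** Sections 12.1 and 12.2 do not exclude patients dialysed after transplant and before randomisation. Sections 11.3.2, 19.3, 19.5 and 19.6 contain no rule for such dialysis.

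**Inputs.** From the protocol: 25 per arm (section 19.1); chi-square test for categorical data and a 0.05 threshold (section 19.5), taken here as two-sided. There is no planned rate, effect size or power to reproduce. Assumed:
- b, the placebo rate of delayed graft function counted from transplant;
- f, the share of placebo events in which dialysis occurred only before randomisation, with the resulting rate b × f the same in both arms;
- r, the true risk ratio for the remaining events.

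**Formulas** (placebo v active).
- From transplant: b v b × [f + (1 − f) × r].
- After randomisation only: b × (1 − f) v r × b × (1 − f).
- Risk difference under both counts: (1 − r) × b × (1 − f).
- Standard error: √[p₀(1 − p₀)/25 + p₁(1 − p₁)/25].

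**Results for b = 0.30, r = 0.50.**

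| f | From transplant | Risk ratio | After randomisation | Risk ratio | Risk difference, both (points) | SE, from transplant (points) | SE, after randomisation (points) |
|---|---|---|---|---|---|---|---|
| 0.05 | 30.0% v 15.75% | 0.525 | 28.5% v 14.25% | 0.50 | 14.25 | 11.7 | 11.4 |
| 0.20 | 30.0% v 18.0% | 0.60 | 24.0% v 12.0% | 0.50 | 12.0 | 12.0 | 10.7 |
| 0.33 | 30.0% v 19.95% | 0.665 | 20.1% v 10.05% | 0.50 | 10.05 | 12.2 | 10.0 |

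For example, at f = 0.20 from transplant: √(0.30 × 0.70/25 + 0.18 × 0.82/25) = √0.014304 = 0.120. After randomisation: √(0.24 × 0.76/25 + 0.12 × 0.88/25) = √0.01152 = 0.107.

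**Wider range.** Four placebo rates (20%, 30%, 40%, 50%), two risk ratios (0.50, 0.75) and the three values of f give 24 scenarios. The standard error falls in all of them, by 0.1 to 2.1 points.

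**Power** (exact enumeration, Pearson chi-square without continuity correction). At b = 0.30 and r = 0.50, from-transplant v after-randomisation power is 23.4% v 24.4%, 17.6% v 20.6% and 13.6% v 17.5% for the three values of f. Across the 24 scenarios the change runs from −0.7 points (b = 0.50, r = 0.75) to +4.8 points (b = 0.40, r = 0.50, f = 0.33).

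If f = 0 the two counts coincide.

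**The case against.** The strongest reply is that the endpoint is valid as written. Allocation is random and blinded, events before randomisation are balanced in expectation, and the from-transplant count answers a legitimate question about the incidence of delayed graft function in the first week. A count after randomisation is a different estimand with its own flaws: a graft that did need dialysis becomes a non-event, an early session may remove the need for a later one, and the observation window varies from 6 to 7 days. All of this stands, and it is why the stated endpoint should stay.

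The numbers also rest wholly on assumption. Nothing in the protocol supports f of 20% or 33%; at f = 5% the effect is slight. That stands too.

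A reader might infer that chance imbalance in these early events is a further harm. It is not, because it is part of the same sampling error. At 30% placebo delayed graft function and f = 20%, the arms differ by two or more such events 35% of the time. With 30% delayed graft function in both arms, however, total counts already differ by two or more 64% of the time.

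Finally, the dialysis times should be recoverable. Section 9.2 expects patients to be inpatients for the first 5-7 days, and section 20.6 makes the full medical record source data. Recoverable is not the same as planned, though, and a count chosen after unblinding would be post hoc.

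**Conclusion.** The point holds as a minor one. The definition admits events that precede allocation, and the document provided does not separate them. The effect is dilution of the risk ratio plus some added noise. With 30% placebo delayed graft function and a true risk ratio of 0.50, a 5% share moves the observed risk ratio to 0.525 and a 20% share moves it to 0.60. The real size is unknown and may be near zero.

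Three stronger readings are not supported. The definition does not bias one arm against the other. Power is not a reason to change it, since power moves little and sometimes falls. It also cannot be said that the plan overlooks the matter altogether: section 19.3 points to an SAP for full details, and if that is a separate document its handling is unknown.

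The unchanged risk difference rests on the proportion dialysed only before randomisation being the same in both arms. That is a simplification, because whether a patient dialysed early is dialysed again is settled after allocation.

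**What to change.** First check whether a separate SAP already covers this. If not:

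1. Keep delayed graft function from transplant as the stated secondary endpoint.
2. Record the times of randomisation, first dose and each dialysis session to day 7, from inpatient records and, for anyone discharged sooner, the routine clinic record.
3. Prespecify, before unblinding, a supporting analysis of any dialysis after randomisation up to day 7 post-transplant, with all analysed patients in the denominator. Do not make it the sole estimate of treatment effect.
4. Report dialysis between transplant and randomisation by arm as a baseline characteristic.

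The cost is a few lines of wording and some times taken from existing records, with no extra visits or samples. The downside is one more analysis of a secondary endpoint, with the limitations of that count described above; reporting both counts lets readers weigh them.
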